11.3.2 Exclusion Criteria

Refer to the core protocol (Section 5.2).

11.3.3 Lifestyle Considerations

Patients must comply with the restrictions described in the core study protocol (Section 5.3).

11.3.4 Concomitant Medications

Patients must comply with the restrictions described in the core study protocol (Section 6.5)

11.3.5 Screen Failures

Refer to the core protocol (Section 5.4).

11.4 STUDY TREATMENT - MODULE 1

Information on the preparation, handling, storage, accountability of study treatment measures

to minimise bias, and study treatment compliance and accountability is either provided in **Table 15** and/or referenced in the core protocol (Section 6).

11.4.1 Study Treatment – AZD0466

The study treatment investigational AZD0466 is described in **Table 15**.

Table 15 Study Treatment for Module 1

Study Treatment	AZD0466
Dosage Form	‘AZD0466 powder for concentrate for solution for infusion’ supplied with ‘Solvent for AZD0466 powder for concentrate for solution for infusion’.
Unit Dose Strength(s)	‘AZD0466 powder for concentrate for solution for infusion’: 500 mg per vial ^a ‘Solvent for AZD0466 powder for concentrate for solution for infusion’: 20 mL per vial ^a
Dose Level	As per dose escalation schema (Section 11.1.3.1)
Route of Administration	Intravenous
Handling Instructions	Refer to Handling Instructions
Provider	AstraZeneca R&D
Packaging and Labelling	AZD0466 powder for concentrate for solution for infusion will be provided in 500 mg vials. Each vial will be labelled as per country requirement. Solvent for AZD0466 powder for concentrate for solution for infusion will be provided in 20 mL vials. Each vial will be labelled as per country requirement.

^a AZD0466 powder for concentrate for solution for infusion 500 mg/vial is intended to be reconstituted with 20 mL custom solvent to produce AZD0466 concentrate for solution for infusion, 25 mg/mL. If required, AZD0466 concentrate for solution for infusion may be further diluted with custom solvent to produce AZD0466 solution for infusion for clinical dosing. Multiple vials of drug product and custom solvent may be used to achieve the required doses.

The dosing and dose escalation scheme are described in Section 11.1.3.1 and the SoA of this module (Section 11.5.1).

Treatment with AZD0466 will commence with a one-week ramp-up followed by weekly administration at the target dose. During ramp-up and while patients are considered at risk of TLS, patients must commence oral allopurinol and encouraged to drink 1.5 to 2 L of fluids at least 24 hours prior to AZD0466 infusion (Appendix F). Intravenous hydration is given on admission as outlined in Appendix F.

This intra-patient dose ramp-up comprises a starting dose on Day 1, subsequent titration to the intermediate dose on Day 4, and to the target dose on Day 8, with weekly IV administration thereafter at the target dose.

The duration of Cycle 1 is 35 days and consists of the 7-day dose ramp-up followed by 28 days of observation during weekly administration at the target dose level (35-day DLT evaluation period, Section 11.4.7). Subsequent cycles are 28 days in duration in which AZD0466 is administered once weekly. All patients will be treated until progressive disease, unacceptable toxicity or withdrawal of consent.

11.4.2 Preparation, Handling, Storage, and Accountability of Study Treatment

Refer to the core protocol (Section 6.2).

11.4.3 Measures to Minimise Bias

Refer to the core protocol (Section 6.3).

11.4.4 Study Treatment Compliance

Refer to the core protocol (Section 6.4).

11.4.5 Concomitant Therapy

Refer to the core protocol (Section 6.5).

11.4.6 Dose Modification

Refer to the core protocol (Section 6.6).

11.4.7 Dose-limiting Toxicity

11.4.7.1 Definition of DLT-evaluable Patients

A DLT-evaluable patient is defined as a patient that has received AZD0466 in Part A and either:

- Has completed the 35-day DLT evaluation period in Cycle 1 and has received at least 75% (3 doses at target dose from Day 8 to Day 29) of the total amount of the planned dose of AZD0466

Or

- Has experienced a DLT during the 35-day DLT evaluation period in Cycle 1.

Patients who have not had a DLT but do not complete the 35-day DLT evaluation period may be replaced to achieve the required minimum number of DLT-evaluable patients for each cohort (Section 11.1.3.4). All DLT-evaluable patients enrolled during the dose-escalation stage will be evaluated in order to determine the MTD and RP2D.

11.4.7.2 Dose-limiting Toxicity

Any event that meets the DLT criteria in the opinion of the Investigator should be reported to the Medical Monitor within 24 hours of knowledge of the event. Events will be assessed for DLT criteria according to the CTCAE National Cancer Institute (NCI) v5.0 (Section [8.3.2](#)) except for TLS, which will be assessed for DLT criteria using the Howard modification of Cairo-Bishop criteria ([Appendix G](#)). Toxicity that is clearly and directly related to the underlying malignancy or to an extraneous cause is excluded from the definition of a DLT. A DLT will be defined as the occurrence of any of the following:

- Any CTCAE Grade 3 non-haematological toxicity lasting > 7 days OR any CTCAE Grade 4 non-haematological toxicity, with the exception of:
 - CTCAE Grade 4 nausea, vomiting, or diarrhoea lasting < 7 days in the absence of maximum supportive therapy,
 - Elevation in serum amylase and/or lipase without clinical or radiographic evidence of pancreatitis,
 - CTCAE Grade 3 fatigue, asthenia, fever, anorexia, or constipation.
- Any other cardiac findings of CTCAE Grade ≥ 2 if considered by the Investigator to be clinically significant.
- AZD0466 should be permanently discontinued if a CTCAE Grade ≥ 3 cardiac AE of any duration occurs at any time during study treatment, if considered by the Investigator to be related to study treatment.
- AZD0466 should be permanently discontinued if liver function test abnormalities meets Hy's Law (HL) or Potential Hy's Law (PHL) criteria, and considered by the Investigator to be related to study treatment (see [Appendix E](#)).
- Prolonged myelosuppression: as myelosuppression and cytopenias are expected outcomes of leukaemia treatment, only the criteria defined below will be a DLT:
 - Lack of haematological recovery (ANC remaining $<0.5 \times 10^9/L$, platelets remaining $< 50 \times 10^9/L$) in the absence of active leukaemia in bone marrow (blasts $< 5\%$) and with marrow hypocellularity at $< 5\%$ by Day 42.
- Cairo-Bishop Grade ≥ 3 Clinical TLS ([Appendix G](#)) that occurs despite protocol-recommended management.
- Cairo-Bishop Laboratory TLS ([Appendix G](#)) with metabolic abnormalities that do not resolve within 5 days despite protocol-recommended management.
- Any other toxicity that
 - is greater than at baseline, is clinically significant and/or unacceptable, and is judged to be a DLT by the SRC, or
 - results in a disruption of dosing schedule of more than 21 days.

Dose-limiting toxicities will not include the following:

- Transient isolated laboratory abnormalities, which are not considered clinically significant and resolve to baseline within 72 hours without any intervention.
- Any documented infection (including COVID-19), bleeding or other direct complication of cytopenia due to active underlying disease.

The DLT evaluation period remains at 35 days for patients with active bone marrow disease by Day 35, irrespective of the blood counts. The DLT evaluation period may be extended to include a repeat bone marrow assessment on Day 42, in the event of myelosuppression (see [Table 6](#)).

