11.7.3 Populations for Analyses

The following populations for analyses are defined in [Table 21](#).

Table 21 **Populations for Analysis**

Population/Analysis set	Description
Safety	All patients who received at least one dose of AZD0466
Intention-to-treat	All patients who received at least one dose of AZD0466
Evaluable for Response	All patients who have received at least 3 doses of AZD0466 at the target dose level in Cycle 1
DLT-evaluable	Patients enrolled in the dose-escalation that have received at least 3 doses of AZD0466 at the target dose level (75% of target doses from Day 8 to Day 29 in Cycle 1) and have completed the safety follow-up through the DLT evaluation period Or Have experienced a DLT
Pharmacokinetics	Dosed patients with at least one reportable plasma concentrations and no important AEs or protocol deviations that may impact PK

AE, adverse event; DLT, dose-limiting toxicity; PK, pharmacokinetics.

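### The DLT for a dosing disruption of more than 21 days cannot be completed by Day 35 when dosing stops after the second target dose, and unless another DLT route applies the patient is then not DLT-evaluable

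*Protocol*

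**What the plan says.** Protocol 11.4.7.2 lists, among other DLT criteria, a toxicity that "results in a disruption of dosing schedule of more than 21 days".

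Protocol 11.4.1 sets the calendar. After ramp-up doses on Days 1 and 4, the patient goes "to the target dose on Day 8, with weekly IV administration thereafter at the target dose", so target doses are due on Days 8, 15, 22 and 29. The same section says: "The duration of Cycle 1 is 35 days and consists of the 7-day dose ramp-up followed by 28 days of observation".

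Protocol 11.4.7.1 gives two routes to being DLT-evaluable. One is to complete the 35 days with at least three of the four target doses. The other is that the patient "Has experienced a DLT during the 35-day DLT evaluation period in Cycle 1". It adds: "Patients who have not had a DLT but do not complete the 35-day DLT evaluation period may be replaced". Protocol 7.2 makes replacement certain only for patients who are withdrawn and not evaluable.

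SAP Table 5 repeats the 35-day limit. SAP 4.14.2 uses for the MTD only DLTs that occur up to Day 35. Protocol Table 21 (11.7.3) differs: its exposure route is "Patients enrolled in the dose-escalation that have received at least 3 doses of AZD0466 at the target dose level", but its other route reads only "Have experienced a DLT", with no time limit.

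Protocol 11.4.7.2 allows the window to be extended for myelosuppression, to Day 42, and for nothing else. No section says whether the 21 days run from the last dose given or from the first missed dose, or whether this DLT is dated by onset of the toxicity or by the day the gap passes 21 days.

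**The concern.** The disruption criterion is there to catch toxicity that keeps a patient off drug. A gap of more than three weeks inside a five-week window can be completed only if dosing stops early. A patient stopped by toxicity after the second target dose has too few doses to be evaluable by exposure, and cannot complete the gap in time to be evaluable by DLT. Under the stated rules that patient leaves both numerator and denominator, and any replacement is a patient who either tolerated treatment or had a DLT that matured sooner. The DLT rate that drives Table 10 and the isotonic MTD estimate is then too low, and an understated rate errs toward higher doses.

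**Working it through.** **Inputs.** Target doses on Days 8, 15, 22 and 29, and a 35-day window (Protocol 11.4.1). Gap of more than 21 days (11.4.7.2). At least three target doses (11.4.7.1, Table 21, SAP Table 5). Decision cells from Protocol Table 10.

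**The plan's own figures.** 3 / 4 = 75%, and 7 + 28 = 35 days. Both reproduce.

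**Calendar.** A gap first exceeds 21 days on its start day + 22.

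| Target doses received | Last dose → gap > 21 days | First missed dose → gap > 21 days | Position at Day 35 |
|---|---|---|---|
| 0 | Day 4 → Day 26 | Day 8 → Day 30 | criterion met on both counts |
| 1 | Day 8 → Day 30 | Day 15 → Day 37 | met only if counted from the last dose |
| 2 | Day 15 → Day 37 | Day 22 → Day 44 | not met on either count; too few doses |
| 3 | Day 22 → Day 44 | Day 29 → Day 51 | not met on either count; evaluable by dose |

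In the two-dose row, only 35 − 15 = 20 or 35 − 22 = 13 days have elapsed by Day 35. Exposure is 2 / 4 = 50% of target doses. Counted in mg with the ramp-up doses, using the Protocol Table 22 dose rows, it runs from (75 + 150 + 2 × 300) / (75 + 150 + 4 × 300) = 825 / 1425 = 57.9% to (2400 + 3600 + 2 × 5400) / (2400 + 3600 + 4 × 5400) = 16800 / 27600 = 60.9%. All are below 75%.

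This is the nominal schedule. If the Day 15 dose were given two days early, on Day 13, the count from the last dose would reach 13 + 22 = Day 35 exactly.

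**Effect on Table 10 of losing one would-be DLT.**
- Replaced by a patient without a DLT: 1/3 (stay) becomes 0/3 (escalate); 2/3 (de-escalate) becomes 1/3 (stay); 2/6 (stay) becomes 1/6 (escalate).
- Excluded and not replaced: 2/6 (stay) becomes 1/5 (escalate).

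**Illustrative size.** Let p be the true DLT rate and q the share of DLTs lost by this route, with no other informative exclusions. The rate among evaluable patients is p(1 − q) / (1 − pq). The documents give no value for q; 10% to 30% is assumed.

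| True p | q = 10% | q = 20% | q = 30% |
|---|---|---|---|
| 30% | 27.8% | 25.5% | 23.1% |
| 40% | 37.5% | 34.8% | 31.8% |

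For example, 0.40 × 0.90 / (1 − 0.04) = 0.36 / 0.96 = 37.5%. At a true rate of 40%, the chance of 0/3, which means escalate, is 0.6³ = 21.6%. It rises to 24.4%, 27.7% and 31.7% for the three values of q.

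**The case against.** The strongest reply is that the toxicity is the DLT and the length of the gap only qualifies it. Dated by onset, a toxicity that starts between Day 15 and Day 22 lies inside the window even if the gap matures later. The protocol already accepts one DLT confirmed after Day 35 (prolonged myelosuppression, Day 42), and Table 21 sets no time limit. This reading is open, but nothing states it, and the only extension granted is for myelosuppression. A reader might infer that the criterion can never operate. The documents do not support that: it works for stops before the first target dose and, on one way of counting, after it.

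Second, most toxicities that stop dosing are DLTs by another route: Grade 3 non-haematological toxicity beyond 7 days, Grade 4, clinically significant cardiac findings, TLS, or SRC judgement, which needs no duration. Haematological dose modifications are not allowed in the first 35 days (Protocol 6.6.1). This stands and narrows the point. What remains is, for example, recurrent or persisting Grade 2 events, Grade 3 events that ease to Grade 2 within 7 days without resolving further, and the exempted Grade 3 terms (fatigue, asthenia, fever, anorexia, constipation). Protocol Table 7 can hold dosing for these. The SRC route is a real safeguard, but a discretionary one.

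Third, a reader might infer that every patient stopped by target-dose toxicity is removed and replaced. That goes too far. A patient with three target doses stays evaluable, and replacement under 11.4.7.1 is optional. Protocol 7.2 makes it certain only for withdrawn, non-evaluable patients. A patient on hold who stays to Day 35 with two target doses is not addressed directly. The distortion comes from the exclusion, with or without replacement.

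**Conclusion.** The point holds in a bounded form. On the nominal schedule, a stop after the second target dose cannot complete this criterion by Day 35 on either count. A stop after the first target dose can do so only if counted from the last dose. Under 11.4.7.1, SAP 4.14.2 and SAP Table 5, such a patient is not DLT-evaluable at Day 35 unless another DLT criterion or SRC judgement applies.

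A reader might infer that a lower observed rate leads to a lower MTD. It is the reverse: 11.4.7.3 selects the dose whose estimated rate is nearest 30%, so an understated rate favours higher doses, which is the unsafe direction.

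The size cannot be derived from the documents. The Table 10 changes show that one patient can matter; the rates above rest on an assumed q. Nor do the documents show that any dose decision in this study was affected. The study was terminated (SAP 1) and SAP 4.14.3 leaves the MTD evaluation out of the analysis. The consequence for reporting is confined to the DLT summaries, which still use the DLT-evaluable set.

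**What to change.** Reconcile Protocol 11.4.7.1, 11.4.7.2 and Table 21 with SAP 4.14.2 and SAP Table 5 on two facts: when the 21-day count starts, and how this DLT is dated. Table 21 should carry the same time limit as the rest.

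For the analysis, attribute this DLT to the window when the causative toxicity begins within the 35 days. Treat a patient on a toxicity hold with fewer than three target doses as pending, neither excluded nor replaced, until dosing resumes or the gap exceeds 21 days. None of this changes when treatment is held or stopped.

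The cost is wording and a possible wait. For a stop after the second target dose, the cohort decision could move from Day 35 to Day 37 or Day 44 (2 or 9 days). Protocol 11.4.7.6 already lets the SRC defer while ongoing patients become evaluable.

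Because the study has ended, the practical step is in the CSR: identify beside the DLT summary any Part A patient whose dosing was stopped for toxicity with fewer than three target doses and who was left out of the DLT-evaluable set, and state how long the gap lasted.

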11.4.7.3 Definition of Maximum Tolerated Dose

The MTD evaluation will be based on the DLT-evaluable population. The MTD will be determined by isotonic regression analysis applied to DLT rates observed during the dose-escalation phase. The estimated MTD will be selected as the dose with the smallest absolute value of difference between the estimated DLT rate and the target DLT rate of 30% among all doses. If 2 or more doses tie for the smallest difference, the following rules will be applied:

- If the estimated DLT rate is < 30% for all doses, then select the higher dose among the tied doses.
- In the case of dose levels with estimated toxicity of equal distance from the target toxicity of 30% (tied dose levels), the following approach will be used ([Ji et al 2010](#)); among all tied dose levels the highest dose level with target toxicity \leq 30% will be selected, unless all tied dose levels have estimated toxicity > 30%, in which case the lowest dose level will be selected.
- If the estimated DLT rate is > 30% for all doses, then select the lower dose among the tied doses.

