11.1.3.3 Dose Escalation, De-escalation, and Stopping Decision Rules

A SRC (Appendix A 5) will be responsible for making recommendations for dose-escalation or de-escalation after each dose level, including decisions on opening cohorts for backfill, in accordance with the SRC charter. The intra-patient dose ramp-up and/or dose schedule for each cohort may be modified based on safety, PK, and PD findings of a previous dose level. The SRC will also assess all evaluable patients to establish the recommended Phase II dose (RP2D) and determine if the study should progress to Part B.

A recommended dose level for each subsequent cohort of patients will be made by the SRC, guided by pre-defined decision rules. The decision rules are based on a mTPI-2 design (Guo et al 2017) with a 30% ($\pm 5\%$) target DLT rate for maximum tolerated dose (MTD). Depending on the number of patients treated at a dose level, and the number of DLTs observed in those patients, the possible decisions will be: to escalate, stay at current dose, de-escalate, or de-escalate and do not use current dose again due to unacceptable toxicity. Decision rules based on mTPI-2 for dose escalation are shown in [Table 10](#).

The decisions on the adequacy of the dose escalation portion of the design were based on outcomes from an internal AZ simulation package which calculates estimates of the likelihood of selecting the true MTD under a range of different scenarios. Operating characteristics are

presented in Table 11.

Table 10 Decision Rules Based on mTPI-2 for Dose Escalation

Number of DLTs	Number of Patients Treated at Current Dose Level											
	n = 1	n = 2	n = 3	n = 4	n = 5	n = 6	n = 7	n = 8	n = 9	n = 10	n = 11	n = 12
0	S ^a	S ^a	E	E	E	E	E	E	E	E	E	E
1	S ^b	S ^b	S	S	E	E	E	E	E	E	E	E
2		DNT	D	D	D	S	S	E	E	E	E	E
3			DNT	DNT	D	D	D	S	S	S	S	E
4				DNT	DNT	DNT	D	D	D	D	D	D
5					DNT	DNT	DNT	DNT	DNT	D	D	D
6						DNT	DNT	DNT	DNT	DNT	DNT	D
7							DNT	DNT	DNT	DNT	DNT	DNT

^a Adapted from [Guo et al 2017](#) from E to S as a minimum of 3 evaluable patients are needed to make a dose escalation decision.

^b Adapted from [Guo et al 2017](#) from D to S as a minimum of 3 evaluable patients are needed to make a dose de-escalation decision.

D, de-escalation to the next lower dose level; DLT, dose -limiting toxicity; DNT, dose not tolerated; E, escalation to the next higher dose level; mTPI-2, modified toxicity probability interval; S, stay at the current dose level.

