11.4.7.5 Definition of Maximum Feasible Dose

A dose and schedule will be considered non-feasible and escalation will cease where the maximum dose permitted based on the Chemistry Manufacturing and Controls (CMC) quality specifications (currently set against a maximum weekly dose of 6000 mg) has been reached.

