11.7.5 General Considerations

For the dose escalation, Part A, a final analysis will be performed when the MTD has been determined and the last patient to be recruited (including any backfill patients) has had the opportunity to complete 2 cycles of treatment, or has discontinued or withdrawn from treatment. Response and survival data will continue to be collected for ongoing patients until this milestone is reached for the final patient.

For Part B, an IA will be performed when the twelfth patient has had the opportunity to complete one cycle of treatment and is response evaluable as per [Table 21](#). This analysis will include evaluation of clinical response and AEs leading to discontinuation. Provided recruitment is not stopped due to futility or safety concerns, a second IA will be performed once all patients recruited have had the opportunity to complete one cycle of treatment, with efficacy analyses based on the ITT population. The final analysis of the expansion cohorts will be undertaken when either the last patient from all expansion cohorts has had the opportunity to complete 6 months of treatment, or all patients have withdrawn from the study or died. Thereafter, patients who are still on study treatment may remain on treatment and individual patients will continue to be assessed for safety as specified in the protocol.

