4.14.3 Definition of Maximum Tolerated Dose and Definition of Recommended Phase II Dose

The MTD evaluation will be based on the DLT-evaluable population. The MTD will be determined by isotonic regression analysis applied to DLT rates observed during the dose-escalation phase. The estimated MTD will be selected as the dose with the smallest absolute value of difference between the estimated DLT rate and the target DLT rate of 30% among all doses. If 2 or more doses tie for the smallest difference, the following rules will be applied:

If the estimated DLT rate is < 30% for all doses, then select the higher dose among the tied doses

If the estimated DLT rate for the tied doses are a combination of < 30% and > 30% then select the higher dose among the tied doses

If the estimated DLT rate is > 30% for all doses, then select the lower dose among the tied doses.

The MTD evaluation will not be part of this analysis and thus related methods are not further be described in this analysis plan. The RP2D and schedule will be determined in discussion among the SRC (Appendix A 5 of the study protocol) and the sponsor. Observations related to PK, PD, and AEs may be included in the rationale supporting the RP2D and schedule.

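### The MTD rule has no 'not reached' outcome, so when every estimated DLT rate is below 30% it names the highest dose tested as MTD, even with no DLTs

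*Protocol*

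**What the plan says.** Protocol 11.4.7.3: "The MTD will be determined by isotonic regression analysis applied to DLT rates observed during the dose-escalation phase". It continues: "The estimated MTD will be selected as the dose with the smallest absolute value of difference between the estimated DLT rate and the target" of 30%, over all doses. The tie rules follow, including "If the estimated DLT rate is < 30% for all doses, then select the higher dose among the tied doses". SAP 4.14.3 repeats the criterion: "The estimated MTD will be selected as the dose with the smallest absolute value of difference". Neither section sets a minimum estimate or describes a result in which no MTD is found.

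Table 10 in Protocol 11.1.3.3 gives the mTPI-2 decisions for a 30% target with a half-width of 5 percentage points. Its legend defines "E, escalation to the next higher dose level". With 0 DLTs it reads E for every n from 3 to 12. With 1 DLT it reads S at n = 3 and 4, and E from n = 5 to 12.

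Escalation can also end for a reason unrelated to toxicity. Under Protocol 11.4.7.5, "A dose and schedule will be considered non-feasible and escalation will cease" once the manufacturing limit is reached, currently 6000 mg weekly. For Part A, Protocol 11.7.5 says "a final analysis will be performed when the MTD has been determined" and the last patient has had the chance of two cycles.

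MTD is a Part A primary endpoint (Protocol 11.2.1, SAP 6.1). SAP 8.12 says an MTD will be reported if one is determined, without saying when that is. SAP 4.14.3 says the MTD evaluation is outside the present analysis.

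**The concern.** An MTD is meant to be the dose at which the DLT rate is near the 30% target. A rule that takes the nearest estimate, however far below 30%, gives that label to the top dose of a trial that never approached the target. The protocol's own escalation table would read the same data as a reason to go higher.

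What is at stake is the meaning of a primary endpoint. A reader who sees an MTD will take it that a toxicity ceiling was located, when escalation may simply have stopped at a supply limit. The trigger in Protocol 11.7.5 has the same gap, since it assumes an MTD will always be found.

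**Working it through.** **Inputs.** Target 30%, interval 25% to 35% (Protocol 11.1.3.3). Isotonic regression and the nearest-to-30% choice (11.4.7.3). Between 3 and 12 evaluable patients per level and about 36 in total (11.1.3.2, 11.7.2.1). Six dose levels (Protocol Table 4, leaving aside DL-1).

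**1. Table 10 reproduced.** Use mTPI-2 with a Beta(1,1) prior (assumed) and intervals of width 0.10 around 25-35%. For 0/3 the posterior is Beta(1,4), with distribution function 1 - (1-p)^4:
- 5-15%: 0.95^4 - 0.85^4 = 0.8145 - 0.5220 = 0.2925
- 15-25%: 0.5220 - 0.3164 = 0.2056
- 25-35%: 0.3164 - 0.1785 = 0.1379

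The largest mass lies below the target, hence E. All 20 cells for 0 or 1 DLT at n = 3 to 12 reproduce, and 66 of the 70 cells at n of 3 or more. The four that differ (2/8, 3/8, 3/12, 4/12) are near-ties between adjacent intervals.

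**2. The rule always names the top dose when all estimates are below 30%.** Isotonic estimates never fall as dose rises, so the distance to 30% never grows as dose rises. The top dose is then nearest or joint nearest, and a tie goes to the higher dose. A check on 48,537 random data sets of this kind gave the top dose every time.

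**3. Examples.**

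| Data | Estimate at DL6 | Named MTD | Table 10 at DL6 |
|---|---|---|---|
| 0/3 at DL1 to DL6 | 0% (all tied) | DL6 | E |
| 0/3 at DL1 to DL5, 1/6 at DL6 | 1/6 = 16.7% (no tie) | DL6 | E |
| 1/6 at DL3, 0/3 elsewhere | 1/(6+3+3+3) = 6.7% (DL3 to DL6 tied) | DL6 | E |

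The second row shows that the nearest-to-30% sentence is the cause. The tie bullet only settles all-zero or pooled cases.

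**4. How often the top dose reads E.** For n = 3 to 12 there are 10 + 9 + 6 + 2 = 27 results below 30% (with 0, 1, 2 and 3 DLTs). Of these, 24 read E and three read S (1/4, 2/7, 3/11). A 1/3 result (33%) also reads S.

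**5. What zero DLTs shows.** The one-sided 95% upper bound is 1 - 0.05^(1/n): 63% at 0/3, 39% at 0/6 and 22% at 0/12. None of these locates a 30% dose.

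**6. Frequency by simulation.** Assumed: cohorts of 3, start at DL1, at most 12 per level and 36 in total. Counted: trials in which the named MTD reads E and no higher dose was found too toxic.
- True rate 5% at all doses: about 99%
- Rising from 1% to 10%: 96-97%
- Rising from 2% to 15%: 84-87%
- DL4 the true MTD: 1-2%

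The spread reflects how many patients are assumed at DL6 before stopping, which the documents do not fix.

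**7. Choice of trigger.** Results below 25% number 10 + 8 + 4 = 22, and all 22 read E. The other two E results below 30% are 2/8 and 3/12. Both equal 25%, inside the protocol's own target interval, and both are near-ties in step 1. The isotonic estimate at the top dose is never below its raw rate. A top-dose estimate under 25% on at least 3 patients therefore always coincides with E.

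**The case against.** The SAP partly covers this. It says the MTD evaluation is not part of the current analysis, and it allows for an MTD that is not determined. The sponsor ended the study after recruitment had stopped with Part A ongoing, and SAP 4.3.1 plans one analysis after database lock. A reader might infer that the stopped study will report a false MTD. The documents do not support that, because the rule is not run. What stands is that no criterion lies behind SAP 8.12's wording and that Protocol 11.4.7.3 is unchanged.

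A reader might also infer that the label would distort the RP2D or later combination dosing. Protocol 11.4.7.4 leaves the RP2D to discussion between the SRC and the sponsor, and PK, PD and adverse events may inform it. Nothing makes it a function of the MTD label. Combination modules would need an amendment.

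The absence of DLTs in the earlier solid-tumour study is weak evidence that this trial would end without DLTs. It covered 9 patients at 50 to 200 mg, against target doses here from 300 mg to an illustrative 5400 mg.

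Finally, it is too broad to say that few DLTs always means escalate: 1/3, 1/4, 2/7 and 3/11 read S. The high frequencies in step 6 also hold only when every true rate is well below 30%.

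**Conclusion.** The point holds in a limited form. The stated rule gives a misleading value for a Part A primary endpoint whenever every isotonic estimate is well below 30%. With no DLTs its conflict with Table 10 is exact at every n from 3 to 12. The ending is foreseeable because the illustrative DL6 target of 5400 mg is close to the 6000 mg feasibility limit.

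The size depends on the unknown toxicity curve: 84% to 99% of simulated trials when true rates stay at or below 15%, and 1-2% when a mid-range dose is the true MTD. These figures rest on the assumed cohort size and stopping number at DL6. Table 11 is redacted and was not used.

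The consequence is confined to what is reported as the MTD. No effect on dosing decisions or the RP2D is shown, and none on the analysis in the current SAP.

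**What to change.** Add to Protocol 11.4.7.3, directly after the nearest-to-30% sentence, and to SAP 4.14.3: if the selected dose is the highest dose evaluated and its isotonic DLT estimate is below 25% (the lower edge of the target interval), report 'MTD not reached; highest dose evaluated = X'. Tie the condition in SAP 8.12 to this criterion. In Protocol 11.7.5, let the Part A final analysis start when the MTD is determined or escalation ends. This concerns reporting only; no dose, escalation step or stopping rule changes.

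An E reading in Table 10 should not be the trigger. In simulation with a true DL6 rate of 30%, it would relabel about 64-74% of DL6 selections, and it would catch 2/8 and 3/12.

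The 25% trigger also has a cost. If the top dose's true rate is 30%, the chance of a raw rate below 25% is:
- n = 6: P(X ≤ 1) = 0.1176 + 0.3025 = 42%, the same as for an E reading.
- n = 12: P(X ≤ 2) = 0.0138 + 0.0712 + 0.1678 = 25%. For an E reading, P(X ≤ 3) adds 0.2397 and gives 49%.

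These are fixed-n figures that ignore pooling and escalation. Among trials that actually select the top dose the share would be higher, because those with many DLTs there select a lower dose. Some trials whose top dose truly is the MTD will therefore report 'not reached', and the result is less definite.
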